5.2.2.2 Adverse event collection and reporting

AE collection

[figure not shown]
Upon enrolment into a trial, the subject's baseline condition is assessed (for instance, by documentation of medical history/concomitant diagnoses), and relevant changes from baseline are noted subsequently.

Subjects will be required to report spontaneously any AEs as well as the time of onset, end, and intensity of these events. In addition, each subject will be regularly assessed by the medical staff throughout the clinical trial and whenever the investigator deems necessary. As a minimum, subjects will be questioned for AEs (and concomitant therapies) at the time points indicated in the [Flow Chart](#). Assessment will be made using non-specific questions such as 'How do you feel?'. Specific questions will be asked wherever necessary in order to more precisely describe an AE.

A careful written record of all AEs shall be kept by the investigator in charge of the trial. Records of AEs shall include data on the time of onset, end time, and intensity of the event as well as any treatment or action required for the event and its outcome.

The following must be collected and documented on the appropriate CRF(s) by the investigator:

- From signing the informed consent onwards until an individual subject's end of trial:
 - All AEs (serious and non-serious) and all AESIs.
 - The only exception to this rule are AEs (serious and non-serious) and AESIs in Phase I trials in healthy volunteers, when subjects discontinue from the trial due to screening failures prior to administration of any trial medication. In these cases, the subjects' data must be collected at trial site but will not be entered in the CRF or trial database and will not be reported in the CTR.
- After the individual subject's end of trial:
 - The investigator does not need to actively monitor the subject for AEs but should only report related SAEs and related AESIs of which the investigator may become aware of by any means of communication, e.g. phone call. Those AEs should, however, not be reported in the CRF.

The REP for BI 1467335, when measurable drug levels or PD effects are still likely to be present after the last administration, is not known for this clinical trial. Therefore, all AEs reported until the end of trial examination (last per protocol contact) will be considered on treatment (please see [Section 7.3.3](#)).

AE reporting to sponsor and timelines

The Investigator must report SAEs, AESIs, and non-serious AEs which are relevant for the reported SAE or AESI, on the BI SAE form via fax immediately (within 24 hours) to the sponsor's unique entry point (country specific contact details will be provided in the ISF). The same timeline applies if follow-up information becomes available. In specific occasions the Investigator could inform the sponsor upfront via telephone. This does not replace the requirement to complete and fax the BI SAE form.

With receipt of any further information to these events, a follow-up SAE form has to be provided. For follow-up information the same rules and timeline apply as for initial information.

Information required

For each AE, the investigator should provide the information requested on the appropriate eCRF pages and the BI SAE form, if applicable. The investigator should determine the causal relationship to the trial medication.

The following should also be recorded as an (S)AE in the CRF and BI SAE form (if applicable):

- Worsening of the underlying disease or of other pre-existing conditions
- Changes in vital signs, ECG, physical examination and laboratory test results, if they are judged clinically relevant by the investigator.

If such abnormalities already pre-exist prior to trial inclusion they will be considered as baseline conditions and should be collected in the eCRF only.

All (S)AEs, including those persisting after individual subject's end of trial must be followed up until they have resolved, have been assessed as 'chronic' or 'stable', or no further information can be obtained.

5.2.3 Assessment of safety laboratory parameters

For the assessment of laboratory parameters, blood and urine samples will be collected by the trial site at the time points indicated in the [Flow Chart](#) after the subjects have fasted for at least 10 h. Subjects do not have to be fasted for drug screening and for infectious serology at the discretion of the investigator or designee. Fasting is not required at the discretion of the investigator or designee for retests.

The parameters that will be determined are listed in [Tables 5.2.3: 1](#) and [5.2.3: 2](#). Reference ranges will be provided in the ISF.

Manual differential white blood cell count or urine sediment examinations will only be performed if there is an abnormality in the automatic blood cell count or in the urinalysis, respectively.

Table 5.2.3: 1 Routine laboratory tests

| Functional lab group | Test name | |
|---|---|-----------|
| Haematology | Haematocrit | |
| | Haemoglobin | |
| | Red blood cell count (RBC) | |
| | Reticulocyte count | |
| | White blood cell count (WBC) | |
| | Platelet count | |
| Automatic WBC differential (relative and absolute) | Neutrophils, eosinophils, basophils, monocytes, lymphocytes | |
| Manual differential WBC (if automatic differential WBC is abnormal) | Polymorphnuclear neutrophils (segs), band neutrophils (stabs), eosinophils, basophils, monocytes, lymphocytes | |
| Coagulation | Activated partial thromboplastin time (aPTT) | |
| | Prothrombin time (Quick's test and INR) | |
| Enzymes | Aspartate transaminase (AST/GOT) | |
| | Alanine transaminase (ALT/GPT) | |
| | Alkaline phosphatase (AP) | |
| | Gamma-glutamyl transferase (GGT) | |
| | Creatine kinase (CK) | |
| | CK-MB, only if CK is elevated | |
| | Lactate dehydrogenase (LDH) | |
| | Lipase | |
| | Amylase (total) | |
| | Thyroid stimulating hormone (TSH) | |
| | | |
| Hormones ¹ Substrates | Serum glucose | |
| | Creatinine | |
| | Total bilirubin | |
| | Direct bilirubin | |
| | Total protein | |
| | Albumin | |
| | Alpha glycoprotein acid | |
| | C-Reactive Protein (CRP) | |
| | Uric acid | |
| | Urea | |
| | Total cholesterol | |
| | Triglycerides | |
| | Electrolytes | Sodium |
| | | Potassium |
| Magnesium | | |
| Calcium | | |

¹ Hormones only at screening and end of trial.

Table 5.2.3: 1 Routine laboratory tests (cont).

| Functional lab group | Test name |
|--|---|
| Urinalysis (Stix) | Urine nitrite |
| | Urine protein |
| | Urine glucose |
| | Urine ketone |
| | Urobilinogen |
| | Urine bilirubin |
| | Urine haemoglobin |
| | Urine leukocytes |
| | Urine pH |
| Urine sediment (microscopic examination if haemoglobin, leukocytes nitrite or protein are abnormal in urine) | Only positive findings will be reported (for instance, the presence of sediment bacteria, casts in sediment, squamous epithelial cells, erythrocytes, leukocytes) |

¹ Hormones only at screening and end of trial.

The tests listed in [Table 5.2.3: 2](#) are exclusionary laboratory tests which may be repeated as required. The results will not be entered in the CRF/database and will not be reported in the CTR. Except for drug screening, it is planned to perform these tests during screening only. Drug screening will be performed at screening and on Day -1 of Visit 2.

Table 5.2.3: 2 Exclusionary laboratory tests

| Functional lab group | Test name |
|---|-----------------------------|
| Drug screening (urine) | Amphetamine |
| | Barbiturates |
| | Benzodiazepine |
| | Cannabis |
| | Cocaine |
| | Methadone |
| | XTC |
| | Opiates |
| | Phencyclidine |
| | Tricyclic antidepressants |
| | Alcohol |
| | Infectious serology (blood) |
| Hepatitis B core antibody (qualitative) | |
| Hepatitis C antibodies (qualitative) | |
| HIV-1 and HIV-2 antibody (qualitative) | |

The laboratory tests listed in [Table 5.2.3: 1](#) and [5.2.3: 2](#) will be performed at the safety laboratory of _____ , _____ .

5.2.4 Electrocardiogram

Twelve-lead ECGs (I, II, III, aVR, aVL, aVF, V1 - V6) will be recorded using a computerised electrocardiograph (Mortara ELI 250 Rx) at the time points given in the [Flow Chart](#).

All ECGs will be recorded for a 10-sec duration after the subjects have rested for at least 5 min in a supine position. ECG assessment will always precede all other study procedures of the same time point (except blood drawing from an intravenous cannula which is already in place) to avoid impact of sampling on the ECG quality.

All ECGs will be stored electronically. Electrode placement will be performed according to the method of Wilson, Goldberger and Einthoven.

All locally printed ECGs will be evaluated by the investigator or a designee. ECGs may be repeated for quality reasons (like alternating current artefacts, muscle movements, electrode dislocation) and the repeated ECG will be used for analysis. Additional (unscheduled) ECGs may be collected by the investigator for safety reasons.

Abnormal findings will be reported as AEs (during the trial) or baseline conditions (at screening) if judged clinically relevant by the investigator. Any ECG abnormalities will be monitored carefully and, if necessary, the subject will be removed from the trial and will receive the appropriate medical treatment.

5.2.5 Assessment of other safety parameters

5.2.5.1 Vital signs

Systolic and diastolic blood pressures (BP) as well as pulse rate (PR) or heart rate (heart rate is considered to be equal to pulse rate) will be measured by a blood pressure monitor (Dinamap Pro 100, GE Medical Systems) at the times indicated in the [Flow Chart](#), after subjects have rested for at least 5 min in a supine position. All recordings should be made using the same type of blood pressure recording instrument on the same arm if possible.

5.2.5.2 Medical examinations

At the screening visit, the medical examination will include documentation of subject information, informed consent, demographics including height and body weight, smoking and alcohol history, relevant medical history and concomitant therapy, review of inclusion and exclusion criteria, review of vital signs (BP, PR), 12-lead ECG, laboratory tests, and a physical examination. At the end of trial examination, it will include review of vital signs, 12-lead ECG, laboratory tests, and a physical examination.

5.4 APPROPRIATENESS OF MEASUREMENTS

All measurements performed during this trial are standard measurements and will be performed in order to monitor subjects' safety and to determine pharmacokinetic parameters in an appropriate way. The scheduled measurements will allow monitoring of changes in vital signs, standard laboratory values, and ECG parameters that might occur as a result of administration of trial medication. The safety assessments are standard, are accepted for evaluation of safety and tolerability of an orally administered drug, and are widely used in clinical trials. The pharmacokinetic parameters and measurements outlined in [Section 5.5](#) are generally used assessments of drug exposure in human mass-balance trials.

5.5 DRUG CONCENTRATION MEASUREMENTS AND PHARMACOKINETICS

Date and clock time of drug administration and pharmacokinetic sampling will be recorded in the eCRF. For drug intake at home the entries from subject's diary will be transferred to the eCRF.

5.5.1 Pharmacokinetic endpoints

5.5.1.1 Primary endpoints

The following primary endpoints will be evaluated for BI 1467335 in plasma after the first dose on Day 1:

- C_{\max} (maximum measured concentration of the analyte after oral administration)
- $AUC_{0-\infty}$ (area under the concentration-time curve of the analyte over the time interval from 0 to infinity after oral administration)
- C_{\max} (maximum measured concentration of the analyte after intravenous administration)
- $AUC_{0-\infty}$ (area under the concentration-time curve of the analyte over the time interval from 0 to infinity after intravenous administration)

The following primary endpoints will be evaluated for BI 1467335 in plasma in the repeated doses treatment group after repeated dosing (Day 28):

- $C_{\max, 28}$ (maximum measured concentration of the analyte after oral administration on Day 28)
- $AUC_{0-24, 28}$ (area under the concentration-time curve of the analyte over the time interval from 0 to 24 h after oral administration on Day 28)
- $C_{\max, 28}$ (maximum measured concentration of the analyte from 0 to infinity after intravenous administration on Day 28)
- $AUC_{0-\infty, 28}$ (area under the concentration-time curve of the analyte from 0 to infinity after intravenous administration on Day 28)

Further assessments will include:

5.5.1.2 Secondary endpoint

The following secondary endpoints will be evaluated for BI 1467335 in plasma:

For (C-14) BI 1467335 and for BI 1467335 after SD and MD

- $t_{\max, t_{\max, 28}}$ (time from dosing to the maximum measured concentration of the analyte)
- $t_{1/2}$, (observed terminal half-life of the analyte) for the oral dose on Day 1
- $t_{1/2}, t_{1/2, 28}$ following the iv dose

For (C-14) BI 1467335 after SD and MD

- CL, CL_{28} (clearance of the analyte)
- $V_z, V_{z,28}$ (volume of distribution of the analyte on Day 1 and on Day 28)

For BI 1467335 after SD and MD

- F (absolute bioavailability) at day 1 and at day 28

Day 1 $(AUC_{0-\infty}/Dose)_{oral}/((AUC_{0-\infty}/Dose)_{iv} * 100$

Day 28 $(AUC_{\tau}/Dose)_{oral}/((AUC_{0-\infty,28}/Dose)_{iv} * 100$

5.5.2 Methods of sample collection

5.5.2.1 Plasma sampling for pharmacokinetic analysis

For quantification of BI 1467335 plasma concentrations, approx. 3 mL of blood will be taken from an antecubital or forearm vein into a K2-EDTA (tripotassium ethylenediaminetetraacetic acid)-anticoagulant blood drawing tube at the times indicated in the [Flow Chart](#).

For quantification of [C-14] BI 1467335 plasma concentrations, an additional 3 mL K2-EDTA tube needs to be collected as indicated in the [Flow Chart](#). Blood will be withdrawn by means of either an indwelling venous catheter or by venipuncture with a metal needle.

All blood samples will be centrifuged

The remaining plasma will be used as analytical back-up sample. Until transfer on dry ice to the analytical laboratory, the plasma samples will be stored frozen and in upright position at about -20°C or below at the clinical site and at the analytical laboratory until analysis.

For detailed description of blood sampling, sample handling, sample preparation, sample storage, tube labelling and sample shipment refer to the laboratory manual.

After completion of the trial the plasma samples may be used for further methodological investigations, e.g. for stability testing, assessment of metabolites. However, only data related to the analyte and/or its metabolite(s) will be generated by these additional investigations. The study samples will be discarded after completion of the additional investigations but not later than 5 years upon the final study report has been signed.

At a minimum, the sample tube labels should list the following information: BI trial number, subject number, visit, planned sampling time, analyte and aliquot. Further information such as matrix may also be provided.

The study samples will be discarded after completion of the additional investigations but not later than 5 years upon the final study report has been signed the analytical laboratory after the bioanalyst has acknowledged safe arrival of the first aliquot.

5.5.3 Analytical determinations

5.5.3.1 Analytical determination of analyte plasma concentration

Cold BI 1467335 concentrations in plasma will be determined by a validated LC-MS/MS (liquid chromatography coupled to tandem mass spectrometry) assay.

[C-14] BI 1467335 will be determined by a validated AMS (accelerator mass spectrometry) assay.

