|-------|-------|---|--|--|-------------------|----------------------|--------------------------------------|-------------|----------------------|---|
| 2 | 28 | 660:00 | 20:00 | | | X | | X | X | ↑ ↓ |
| | | 661:00 | 21:00 | | | | X | | | |
| | 29 | 672:00 | 08:00 | | | X | | | | |
| | | 673:00 | 09:00 | | | | X | | | |
| | 30 | 697:00 | 09:00 | | X | | X | X | X | |
| | 32 | 745:00 | 09:00 | Discharge from trial site | | | X | | | |
| 3 | 33-40 | | | End of trial (EOT) examination ^{6, 9} | X | | | X | X | X |

1. Screening includes subject information, informed consent, physical examination, check of vital signs, ECG, safety laboratory (including drug and virus screening), demographics (including determination of body height and weight, BMI, smoking status and alcohol history), relevant medical history, concomitant therapy and review of inclusion/exclusion criteria.
2. The time is approximate; the procedure is to be performed within a time window of 3 h prior to drug administration. After start of treatment, further PK blood sampling (trough level) within 30 minutes before next scheduled dosing.
3. If several actions are indicated at the same time point, the intake of meals will be the last action.
4. Subjects are to be fasted for at least 10 h before sample is taken.
5. Only urine drug and alcohol screening will be done at this time point.
6. End-of-trial (EOT) examination to be performed on Day 34-41, EOT examination includes physical examination, vital signs, ECG, safety laboratory, recording of AEs and concomitant therapies.
7. On Days 3 to 6, 8 to 13, 15 to 20 and 22 to 25, subjects are allowed to take their study medication at home if deemed appropriate by the investigator. Compliance of medication intake will be monitored by subject diary and daily phone contact between subject and site. The scheduled time for drug intake throughout the study is 08:00 (applies for intake at home and at the trial site).
8. Pharmacogenomic sample.
9. For definition of the individual subject's end of trial see [Section 6.2.3](#).
10. Samples for an individual subject beyond 5 h after end of infusion will be only analyzed if for this subject the plasma level of [C-14]BI 1467335 at this time point (i.e., 6:15) is still above LOQ.
11. Subjects will be hospitalized from admission on Day 25 to Day 32.

TABLE OF CONTENTS

| | |
|--|-----------|
| TITLE PAGE | 1 |
| CLINICAL TRIAL PROTOCOL SYNOPSIS | 2 |
| FLOW CHART | 5 |
| TABLE OF CONTENTS | 8 |

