3.2 DISCUSSION OF TRIAL DESIGN, INCLUDING THE CHOICE OF CONTROL GROUP

Due to the time dependent non-linear kinetics of BI 1467335, systemic exposures on Day 28 cannot be predicted from Day 1 kinetics, (IB [c04751792]). Therefore the absolute oral bioavailability will be determined on two occasions following single (Day 1) and multiple oral dose treatment (Day 28) following 10 mg of BI 1467335 qd (2 film-coated tablets of 5 mg dose strength), the maximum therapeutic dose used in ongoing phase II studies.

The same subject will receive a ¹⁴C labelled microtracer infusion on Day 1 after a single oral dose and on Day 28 after multiple oral doses. Thus, the oral bioavailability on Day 1 and 28 will be calculated for each subject on each day. As the iv infusion is given at the geometric mean t_{max} of the oral dose, this accounts for the observed non-proportionality in systemic exposure observed between Days 1 and 28.

[C-14] BI 1467335 is unlikely to exhibit any detectable isotope effects (see [Section 2.3](#)).

The open-label treatment is not expected to bias results, since the primary study endpoints are derived from quantitative measurements of plasma concentrations of the analyte following oral and iv dosing.

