4. TREATMENTS

4.1 TREATMENTS TO BE ADMINISTERED

BI 1467335 doses are calculated as a free base. 10 mg BI 1467335 free base equals to 11.3 mg BI 1467335 HCl salt.

Radiolabelled BI 1467335 (C-14) (test product 2) is administered as an intravenous solution. The powder used for intravenous solution contains [C-14] BI 1467335 and unlabelled BI 1467335 both manufactured by BI Pharma GmbH & Co. KG. The mixture of [C-14] BI 1467335 and unlabelled BI 1467335 and the solution from this mixture are made by

Unlabelled film coated tablets (test product 1) have been manufactured by BI Pharma GmbH & Co. KG.

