7.2 NULL AND ALTERNATIVE HYPOTHESES

It is not planned to test any statistical hypotheses in a confirmatory sense.

The absolute oral bioavailability of BI 1467335 by comparing 8,85 μg (Day 1) or 5 μg (Day 28) intravenously administered [C-14] BI 1467335 free base with an oral dose of 10 mg of BI 1467335 free base after single and multiple oral doses will be estimated by the ratios of the geometric means (test/reference) for the dose normalized primary PK endpoints.

Additionally, their two-sided 90% confidence intervals (CIs) will be provided. This method corresponds to the two one-sided t-tests procedure, each at the 5% significance level. Confidence intervals will have to be interpreted in the perspective of the exploratory character of the trial, i.e. confidence intervals are considered as interval estimates for effects.

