7.3.1 Primary analyses

The pharmacokinetic endpoints listed in [Section 5.5.1](#) will be calculated according to the BI Standard Operating Procedure (SOP) ‘Standards and processes for analyses performed within Clinical Pharmacokinetics/Pharmacodynamics’ ([001-MCS-36-472](#)).

Plasma concentration data and derived parameters of a subject will be included in the statistical pharmacokinetic (PK) analyses if they are not flagged for exclusion due to a protocol violation relevant to the evaluation of PK (to be decided no later than in the RPM) or due to PK non-evaluability (as revealed during data analysis, based on the criteria specified below). Exclusion of a subject’s data will be documented in the CTR.

Plasma concentrations and/or derived parameters of a subject will be considered as non-evaluable, if for example:

- The subject experiences emesis at or before two times median t_{max} . Median t_{max} is to be taken either from the median t_{max} for the reference product or from median t_{max} for the test product, depending on whether the subject had experienced emesis after taken the test or the reference product. Median t_{max} is to be determined excluding the subjects experiencing emesis.
- Missing samples/concentration data at important phases of PK disposition curve.

The primary PK parameters C_{max} and $AUC_{0-\infty}$ on Day 1 and $C_{max,28}$, $AUC_{0-24,28}$ (after oral administration) and $AUC_{0-\infty,28}$ (after intravenous administration) on Day 28 (refer to [Section 5.5.1](#)) of BI 1467335 in plasma will be dose normalized and then log-transformed (natural logarithm) prior to fitting the ANOVA model. The difference between the expected means for $\log(\text{Test})-\log(\text{Reference})$ will be estimated by the difference in the corresponding least square means (point estimate) and two-sided 90% confidence intervals based on the t-distribution will be computed.

These quantities will then be back-transformed to the original scale to give the point estimator (geometric mean) and 90% confidence interval estimates for the intra-subject ratio of the geometric means for treatments test and reference.

This will be done for Day 1 and Day 28 separately, thus the analysis variables are the following:

| | |
|-------------------------|--|
| Day 1 for C_{\max} : | normalised C_{\max} after oral and intravenous administration |
| Day 1 for AUC: | normalised $AUC_{0-\infty}$ after oral and intravenous administration |

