7.3.5 Pharmacokinetic analyses

The pharmacokinetic parameters listed in [Section 5.5.1](#) for drug BI 1467335 will be calculated according to the relevant SOP of the Sponsor ([001-MCS-36-472](#)).

Subjects who are not included in the PKS (refer to [Section 7.3.1](#)) will be reported with their individual plasma concentrations and individual derived pharmacokinetic parameters; however, they will not be included in descriptive statistics for plasma concentrations, pharmacokinetic parameters or other statistical assessment.

Only concentration values within the validated concentration range and actual sampling times will be used for the calculation of pharmacokinetic parameters. Concentrations used in the pharmacokinetic calculations will be in the same format provided in the bioanalytical report, (that is, to the same number of decimal places provided in the bioanalytical report).

Plasma concentrations will be plotted graphically versus time for all subjects as listed in the drug plasma concentration-time tables. For the presentation of the mean profiles, the arithmetic mean, geometric mean and the planned blood sampling times will be used.

In addition to the analysis described [Section 7.3.1](#), the absolute bioavailability factor F will be calculated for each subject on Day 1 as

$$F = \text{normalised AUC}_{0-\infty} (\text{oral}) / \text{normalised AUC}_{0-\infty} (\text{i.v.})$$

and for each subject on Day 28 as

$$F = \text{normalised AUC}_{0-24, 28} (\text{oral}) / \text{normalised AUC}_{0-\infty, 28} (\text{i.v.})$$

The calculated parameter at Day 1 and Day 28 will be analysed with descriptive statistics.

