7.4 PRIMARY ENDPOINTS

Analysis of absolute oral bioavailability of dose-normalised primary endpoints will be performed as defined in Sections 7.1.3 and 7.3.1 of the CTP.

The statistical model for the primary analysis defined in the CTP is an analysis of variance (ANOVA) model on the logarithmic scale.

Primary PK endpoints will also be assessed descriptively. The analysis of standard PK parameters is performed according to BI standards (5) [001-MCS-36-472_RD-01].

Exclusion of PK parameters

The ADS ADPP contains column variables APEXC and APEXCO indicating inclusion/exclusion (APEXC) of a PK parameter and an analysis flag comment (APEXCO). All analyses based on the PKS are based on PK parameter values which are not flagged for exclusion, i.e. with APEXC equal to 'Included'.

Exclusion of plasma concentrations

The ADS ADPC (PK concentrations per time-point or per time-interval) contains column variables ACEXC or ACEXCO indicating inclusion/exclusion (ACEXC) of a concentration and an analysis flag comment (ACEXCO). Exclusion of a concentration depends on the analysis flag comment ACEXCO. For example, if ACEXCO is set to 'ALL CALC', the value will be excluded for all types of analyses based on concentrations. If ACEXCO is set to 'DESC STATS' the value will be excluded from descriptive evaluations per planned time point/time interval. If ACEXCO contains the addition 'TIME VIOLATION' or 'TIME DEVIATION', the value can be used for further analyses based on actual times. If ACEXCO is set to 'HALF LIFE', the value will be excluded from half-life calculation only; the value is included for all other analyses. Excluded concentration itself will be listed in the CTP trial associated with an appropriate flag.

Further details are given in "Noncompartmental Pharmacokinetic / Pharmacodynamic Analyses of Clinical Studies" ([5](#)) and "Description of Analytical Transfer Files and PK/PD Data Files" ([7](#)).

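### Unlabelled drug from the infusion is counted as tablet drug: each subject's F rises by 0.41 points on Day 1 and by at most 0.45 on Day 28, and the protocol and SAP state no correction

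*Protocol*

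**What the plan says.** The infusion is a mixture. Protocol 4.1 states: "The powder used for intravenous solution contains [C-14] BI 1467335 and unlabelled BI 1467335". The Synopsis and Sections 3.1, 4.1.1 and 6.2.2 give the amounts as free base: 41.15 µg unlabelled plus 8.85 µg labelled on Day 1, and 45 µg plus 5 µg on Day 28.

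Two assays are used. Protocol 5.5.3.1 says "Cold BI 1467335 concentrations in plasma will be determined by a validated LC-MS/MS", and assigns [C-14] drug to accelerator mass spectrometry (AMS). The Flow Chart continues cold sampling through and after the infusion (1:05, 1:25, 2:00 and later, with the same pattern on Day 28).

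For the doses, Protocol 7.2 compares 8.85 µg (Day 1) or 5 µg (Day 28) "intravenously administered [C-14] BI 1467335 free base with an oral dose of 10 mg". SAP Table 6.1: 2 labels the two references by the same [C-14] amounts.

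For the analysis, Protocol 7.3.1 says the primary parameters "will be dose normalized and then log-transformed (natural logarithm) prior to fitting the ANOVA model". Protocol 7.3.5 adds that "the absolute bioavailability factor F will be calculated for each subject on Day 1 as" the ratio of the dose-normalised AUCs, with a parallel formula for Day 28. SAP 7.4 defers to the protocol: "Analysis of absolute oral bioavailability of dose-normalised primary endpoints will be performed as defined in Sections 7.1.3 and 7.3.1 of the CTP". SAP 4 declares no change to the planned analysis. None of these sections removes the infused unlabelled drug from the oral profile.

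**The concern.** LC-MS/MS reports the sum of unlabelled drug from the tablet and from the vein. The infused unlabelled drug is in no intravenous quantity, because that arm is measured and normalised on [C-14] alone. It is in the oral AUC, which is divided by 10 mg as if the tablet had supplied all of it.

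Absolute bioavailability is the primary objective, and this error pushes it in one direction in every subject. It does not shrink with more subjects, and the confidence interval gives no sign of it. Cmax may be affected too. Protocol 3.2 says "As the iv infusion is given at the geometric mean" oral tmax, so the unlabelled infusate arrives when many subjects are near their oral peak.

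**Working it through.** **Inputs.** Infused amounts, the 10 mg (10,000 µg) tablet dose, infusion start 1 h after the tablet and the 15-minute duration come from the protocol sections cited above. Protocol 3.2 expects no detectable isotope effect. The components add up as stated (41.15 + 8.85 = 50; 45 + 5 = 50). The plan gives no figure for this contribution, so there is none to reproduce. It also gives no expected F, half-life or variability in the available text, so those are assumed and shown as ranges.

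**Day 1 AUC.** Let A be a subject's [C-14] AUC0-∞. Labelled and unlabelled drug enter together and are handled alike, so the infused unlabelled drug adds (41.15/8.85) × A = 4.65 × A to the cold AUC. The dose-normalised intravenous AUC is A/8.85. Then

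apparent F = [(tablet AUC + 4.65 × A)/10,000] ÷ (A/8.85) = true F + 41.15/10,000 = true F + 0.41 points.

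A cancels, so the shift is the same whatever the subject's clearance.

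**Day 28 AUC.** The ratio is 45/5 = 9.0 and the ceiling is 45/10,000 = 0.45 points. It is a ceiling because oral AUC stops 24 h after the tablet, which is 23 h after infusion start, while intravenous AUC runs to infinity. For one compartment the share counted is about 1 − exp(−ln 2 × 23/t½):

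- t½ 4 h: 98.1%, giving 0.44 points
- t½ 8 h: 86.4%, giving 0.39 points
- t½ 24 h: 48.5%, giving 0.22 points

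**Relative size** (shift divided by true F):

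| True F | Day 1 | Day 28 (upper bound) |
|---|---|---|
| 50% | 0.8% | 0.9% |
| 20% | 2.1% | 2.3% |
| 10% | 4.1% | 4.5% |
| 5% | 8.2% | 9.0% |

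The bias passes 5% only if F is below 0.4115/0.05 = 8.2% (Day 1) or 0.45/0.05 = 9.0% (Day 28).

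**Effect on the ANOVA ratio.** With lognormal F_i and shift d, the ratio moves by exp(mean log(F_i + d)) − exp(mean log F_i). For an assumed between-subject CV of 20, 30 or 50% this is 0.42, 0.43 or 0.46 points on Day 1 and at most 0.46, 0.47 or 0.50 on Day 28.

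**Check on the planned sampling times.** One-compartment profiles with non-compartmental AUCs at the Flow Chart times (assumed t½ 0.5 to 8 h, absorption rate 1 to 4 per h, F 5 to 80%) gave shifts of 0.406 to 0.411 points on Day 1 and 0.387 to 0.449 on Day 28. Sparse sampling does not alter the result.

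**Day 1 Cmax.** By 1:05, 5 of the 15 infusion minutes have passed, so 41.15 × 5/15 = 13.7 µg of unlabelled drug is in. Inflation of oral Cmax at the planned cold sampling times (one compartment, assumed t½ 1 to 8 h):

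| True tmax | F = 50% | F = 20% | F = 10% |
|---|---|---|---|
| 0.75 h or less | 0 | 0 | about 0.1% at most |
| 1.0 h | 0.3–0.5% | 0.75–1.3% | 1.7–2.7% |
| 1.25 h | 0.9–1.6% | 2.2–4.0% | 4.5–8.1% |

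Over the wider ranges of the sampling-time check, Cmax inflation ran from 0 to about 14%, largest at F = 5%.

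**The case against.** **Materiality.** The trial is exploratory, with 10 to 12 subjects and no acceptance range. The upper 90% limit lies exp(t × s × √(2/n)) − 1 above the estimate, where s = √ln(1 + CV²) and t is the 95th percentile on n − 1 degrees of freedom. For an assumed intra-subject CV of 10 to 30% that is about 8 to 24% at n = 12 and 10 to 32% at n = 8. At F of 20% or more the AUC bias is a small part of that. This stands: the point is minor in size unless F is low. It does not justify leaving a known, one-directional error in a primary endpoint when it can be removed at almost no cost.

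**Recoverable later.** A reader could subtract 0.41 points from each Day 1 F. That is true for Day 1. On Day 28 the amount depends on the subject's [C-14] profile, and Cmax cannot be corrected from published summaries.

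**Unseen material.** The pharmacokinetic SOP (001-MCS-36-472) and the ADS Plan are cited but not available, and either might contain a correction. This stands as a limit on the finding. A trial-specific factor that changes a primary endpoint should still be visible in the SAP.

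**AMS units.** The factors 4.65 and 9.0 assume that AMS results are labelled mass only. If they were total-infusate equivalents, those factors would subtract about 41.15 × 50/8.85/10,000 = 2.3 points on Day 1 and up to 45 × 50/5/10,000 = 4.5 on Day 28. Protocol 5.5.3.1 and 7.2 and SAP Table 6.1: 2 all name [C-14] BI 1467335 as the analyte or reference dose, so the labelled-mass reading is the documented one. Stating the basis costs one clause.

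**Conclusion.** The concern holds. Followed as written, the plan raises every subject's AUC-based F by 0.41 points on Day 1 and by up to 0.45 points on Day 28. The Day 1 figure is a mass balance that rests on three things: no isotope effect, AMS results expressed as [C-14] mass, and an intravenous AUC normalised to the [C-14] dose. The size below the Day 28 ceiling depends on half-life, which is assumed here. The Cmax effect depends on when each subject peaks and will be zero in some.

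In relative terms the AUC error is under 1% if F is 50% and above 5% only if F is below 8.2% (Day 1) or 9.0% (Day 28). It should be corrected, but it does not threaten the trial.

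**What to change.** Add a derivation to Protocol 7.3.1 and 7.3.5 and SAP 7.4, applied per subject before dose normalisation and log transformation, with AMS values expressed as [C-14] mass:

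- **Day 1 AUC:** oral AUC0-∞ = cold AUC0-∞ − 4.65 × [C-14] AUC0-∞.
- **Day 28 AUC:** oral AUC0-24 = cold AUC0-24 − 9.0 × [C-14] AUC from 649:00 to 672:00, interpolating [C-14] to 672:00 between the 661:00 and 673:00 samples. [C-14] AUC0-∞ must not be used here, because it would over-correct.
- **Cmax:** subtract 4.65 × (Day 1) or 9.0 × (Day 28) the [C-14] concentration at the shared samples (1:05, 1:25, 2:00; 649:05, 649:25, 650:00). Interpolate [C-14] if the peak is later, then take the maximum of the corrected values.

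Interpolation and BLQ handling can follow the rules already in force for the non-compartmental analysis. If the SOP already makes this correction, one SAP sentence saying so is enough.

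**Cost.** A short derivation and no new samples. AMS error enters the oral values: an assumed 10% error moves Day 1 oral AUC by 0.1 × 0.82% = 0.08% if F is 50%, and by 0.4% at 10% and 0.8% at 5%. It cancels in the correction to each subject's Day 1 F, which is a constant 0.41 points. Cold and [C-14] sampling times differ after 2:00 on Day 1, and Flow Chart footnote 10 makes late Day 1 results conditional: "Samples for an individual subject beyond 5 h after end of infusion will be only analyzed" if the 6:15 level is still quantifiable. That is why the AUC correction is made on AUCs and not sample by sample.
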